7.4.1 Safety Criteria for Adjustment or Stopping Doses

7.4.1.1 SEL-212 or Placebo

A patient will be withdrawn from study drug for meeting the following stopping rule:

- sUA level < 2.0 mg/dL, measured 1 hour after the infusion of the second component of study drug is completed during Treatment Period 1
- AND
- sUA level > 1.0 mg/dL measured at the Day 21 visit of Treatment Period 1 or sUA level > 6.0 mg/dL at the Day 21 visit of any of Treatment Periods 2-11

Stopping rules will be assessed by an independent, central, unblinded medical monitor.

If withdrawn from study drug during the double-blind treatment period (Treatment Period 1 to 6) or the double-blind extension period (Treatment Period 7 to 12), regardless of reason, the patient will continue study visits to the end of Treatment Period 12.

The window for all Day 21 visits is +2/-1 days. If a Day 21 visit sUA value drawn within the protocol window is not available, but if a sUA value drawn at an unscheduled visit after the Day 21 window is available prior to dosing that is ≤ 1.0 mg/dL during Treatment Period 1 or ≤ 6.0 mg/dL during Treatment Periods 2-11, the patient will not be required to be withdrawn from study drug and will be eligible to receive their subsequent dose.

If 1) a Day 21 visit sUA value drawn within the protocol window is not available and no subsequent sUA results are available or 2) a Day 21 visit sUA value drawn within the protocol window is not available and

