a subsequent sUA drawn at an unscheduled visit after the Day 21 window is > 1.0 mg/dL during Treatment Period 1 or > 6.0 mg/dL during Treatment Periods 2-11, then the patient will be withdrawn from study drug based on the protocol deviation. If a protocol deviation occurs where a patient is not able to be dosed within the dosing day window (for example in the case of COVID-19 restrictions temporarily preventing dosing) the current treatment period will be extended up to a maximum of 90 days without skipping doses for patients with a Day 21 visit sUA value ≤ 1.0 mg/dL during Treatment Period 1 or ≤ 6.0 mg/dL during Treatment Periods 2-11 in the D21 visit window or subsequent up to the rescheduled dosing visit. If this protocol deviation occurs such that the patient was unable to be dosed within the dosing day window for the Treatment Period 7 Day 0 dose, then the Treatment Period 6 Day 28 visit should still occur 28 days (+3/-4 days) after the Treatment Period 6 dose or as close to the visit window as possible to collect the final primary endpoint sUA sample. In this specific instance, the dosing day Treatment Period 7 Day 0 should then occur as soon as possible afterward up to a maximum of 90 days from the preceding dose.

To maintain the blind, a central group of unblinded pre-specified medical personnel will adjudicate the implementation of the stopping rules.

If withdrawn from study drug, the patient will continue study visits to the end of Treatment Period 12. At the discretion of the Investigator, the patient will be permitted to return to ULT 60 days after the patient's last study drug treatment. ULT shall not be SEL-212 or any experimental or marketed uricase (e.g., rasburicase (Elitek, Fasturtec), pegloticase (Krystexxa®), for the remainder of the study.

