During Screening, all patients should be tested for COVID-19 by an FDA Emergency Use Authorized COVID-19 molecular assay for detection of SARS-CoV-2 RNA. A patient with a positive test result is permitted to request re-testing. A patient who requests re-testing should wait at least 10 days after the date of the first positive COVID-19 diagnostic test, as long as no symptoms have developed. If the

second test is positive for COVID-19, then the patient will be excluded from enrollment. If the second test is negative for COVID-19, then the patient must be tested a third time at least 24 hours after the second test to confirm the negative result.

On Study:

Once a patient is enrolled in the study, the investigational site will manage the patient according to its institutional standards and procedures established for COVID-19. During the study, a patient presenting with both symptoms (only severe and critical illness as per definitions below) of COVID-19 and positive COVID-19 test results will be discontinued from study treatment. The patient will be permitted to resume study visits for continued assessments (but not treatment with SEL-212 or placebo) according to the institutional standards and/or procedures of the investigational site.

Patients with mild-moderate COVID-19 illness (as per definitions below) will be allowed to resume study visits (on treatment with SEL-212 or placebo) after resolution of acute symptoms of clinical disease (except for loss of smell and taste) and meeting quarantine requirements so long as their subsequent dose occurs ≤90 days from their prior dosing day as per section 7.4.1.1. Patients with mild-moderate COVID-19 illness can continue **non-dosing study visits** as per protocol mandated visit window prior to resolution of acute symptoms according to the institutional standards and/or procedures of the investigational site.

Enrolled patients in the study with mild-moderate COVID-19 illness can be treated with anti-SARS-CoV-2 monoclonal antibodies. These patients will be allowed to resume study visits (on treatment with SEL-212 or placebo) after 2 weeks of receiving monoclonal antibodies, and confirmation of resolution of acute symptoms of clinical disease (except for loss of smell and taste), and meeting quarantine requirements so long as their subsequent dose occurs ≤90 days from their prior dosing day as per section 7.4.1.1.

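### When the Day 21 sUA is drawn late, the plan applies only half of its two-part stopping rule, so a placebo patient can lose study drug on a value that would not stop them if drawn on time

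*Protocol*

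**What the plan says.** **Main rule.** Protocol 7.4.1.1, which covers SEL-212 and placebo alike, joins two conditions with AND. The first is "sUA level < 2.0 mg/dL, measured 1 hour after the infusion of the second component of study drug is completed during Treatment Period 1". The second is "sUA level > 1.0 mg/dL measured at the Day 21 visit of Treatment Period 1", or a Day 21 value above 6.0 mg/dL in any of TP2-11. The synopsis and the stopping rules in SAP 3.3 repeat this.

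**Missed-draw paragraph.** The same section covers a missing in-window Day 21 value in two limbs.
- No later value: "If 1) a Day 21 visit sUA value drawn within the protocol window is not available and no subsequent sUA results are available".
- A late value above the threshold: "a subsequent sUA drawn at an unscheduled visit after the Day 21 window is > 1.0 mg/dL during Treatment Period 1", or above 6.0 mg/dL in TP2-11.

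For both limbs, "then the patient will be withdrawn from study drug based on the protocol deviation". A late value at or below the threshold keeps the patient on study drug. The 1-hour condition does not appear and no arm is exempted. The synopsis and SAP 3.3 carry the same paragraph, except that the SAP has the patient leaving the study rather than study drug. SAP 3.3 also says that visits continue to the end of TP12 after withdrawal from study drug for any reason.

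**Dosing delay.** If a dose cannot be given in its window, "the current treatment period will be extended up to a maximum of 90 days without skipping doses", but only for patients with sUA at or below 1.0 (TP1) or 6.0 (TP2-11).

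**COVID-19.** Under Protocol 12.1.8.7, patients with mild-moderate illness "will be allowed to resume study visits (on treatment with SEL-212 or placebo) after resolution of acute symptoms of clinical disease", provided that the next dose falls within 90 days of the last. That proviso refers to 7.4.1.1.

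**Estimand.** Protocol 13.4.1 and SAP 6.1 make meeting the stopping criteria a composite failure and send all unlisted intercurrent events to treatment policy. Withdrawal for a missed draw is not listed.

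**The concern.** The 1-hour condition is what keeps placebo patients out of the stopping rule. Placebo is normal saline and entry sUA is at least 7 mg/dL, so a value below 2.0 an hour after infusion is practically impossible on placebo. Without that condition, an ordinary untreated sUA is enough for withdrawal. The late-value limb and the 90-day clause both drop it, so a logistic event (a late draw or a delayed dose) has different consequences by arm.

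What is exposed:
- **Placebo exposure and safety rates.** SAP 10.3 divides events by treatment exposure time, which a placebo withdrawal shortens.
- **Flares, tender joints, SF-36 and HAQ-DI.** Their main estimands use treatment policy for everything except death, and 7.4.1.1 lets a withdrawn patient return to ULT 60 days after the last dose. Placebo results may then include ULT that an on-time draw would not have opened.
- **Estimand class.** A SEL-212 patient who has lost response is a composite failure if the value is on time. If it is late, the withdrawal is labelled a deviation and appears to fall under treatment policy.

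**Working it through.** **1. The plan's own figure.** Inputs from Protocol 13.1: 45% v 5%, two-sided alpha 2.5%, power 90%, chi-square with continuity correction, 1:1 per comparison. The normal-approximation formula gives 27 per arm without the correction and 32 with it, as stated. Allowing for 8% early termination, 32 / 0.92 = 34.8, so 35, also as stated; 40 per arm are planned. None of this depends on the missed-draw paragraph.

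**2. The same value under the two rules.** On time: withdraw if 1-hour TP1 sUA < 2.0 AND value > 1.0 (TP1) or > 6.0 (TP2-11). Late: withdraw if value > 1.0 or > 6.0, or if there is no value. The sUA values are illustrative; placebo is taken near entry level, also at 1 hour.

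| Patient | 1-hour TP1 sUA | Later sUA | Drawn on time | Drawn late |
|---|---|---|---|---|
| Placebo | 7.5 | 7.5 or 6.5 | kept | withdrawn |
| SEL-212 responder | 0.2 | 0.2 | kept | kept |
| SEL-212, response lost | 0.2 | 7.0 | withdrawn | withdrawn |
| Any arm, no value | any | none | not applicable | withdrawn |

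The result is the same for TP1 and TP2-11. The rules differ only for patients whose 1-hour TP1 value was not below 2.0, in practice the placebo arm.

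**3. How many.** The documents give no missed-draw rate, so p per draw is an assumption. Five Day 21 draws (TP1-5) decide the doses of TP2-6.
- If every miss is followed by a late value: 1 - (1 - p)^5.
- If half the misses have no later value (assumption), the late-value limb acts with probability p/2 per draw: 1 - (1 - p/2)^5.

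| p | All misses late-value | Of 40 | Half late-value | Of 40 |
|---|---|---|---|---|
| 2% | 1 - 0.98^5 = 9.6% | 3.8 | 1 - 0.99^5 = 4.9% | 2.0 |
| 3% | 1 - 0.97^5 = 14.1% | 5.7 | 1 - 0.985^5 = 7.3% | 2.9 |
| 5% | 1 - 0.95^5 = 22.6% | 9.0 | 1 - 0.975^5 = 11.9% | 4.8 |

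The second column is an upper bound on the placebo-specific effect. In the half-and-half case SEL-212 responders also lose study drug through the no-value limb, so the excess withdrawal on placebo is 9.6 - 4.9 = 4.7, 14.1 - 7.3 = 6.8 and 22.6 - 11.9 = 10.7 percentage points.

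**4. Primary endpoint.** Placebo response is assumed to be 5%. If these withdrawals lower it at all, it falls to between 0 and 5%. Power at 40 per arm (two-sided 2.5%, no continuity correction) is 98.3% at 5% and 99.9% at 0%. This takes ULT started after withdrawal as a failure under the sUA-lowering-medication item.

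**5. When ULT opens.** With 28-day dosing, a last dose on Day 0, 28, 56 or 84 (TP1-4) allows ULT from Day 60, 88, 116 or 144, all before the Day 168 assessment. A last dose on Day 112 (TP5) gives Day 172, which is after it.

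**The case against.** - **The no-value limb is not arm-specific.** This stands. A reader might infer that missed visits remove placebo patients but never SEL-212 responders. A responder with no later value is withdrawn too, and a SEL-212 patient who has lost response is stopped under either rule.
- **The 10, 14 and 23% are not an arm difference.** This stands. They count every miss, at a rate without a source in the documents. Day 21 assessments may be done remotely (Appendix A), which makes misses less likely.
- **12.1.8.7 need not contradict 7.4.1.1.** This stands. It refers back to 7.4.1.1 and may import the sUA limit, and its mention of both arms may simply name blinded study drug. But if it does import the limit, very few placebo patients could use it. The text does not settle this. The 90-day clause is likewise silent on what happens to a patient above the limit.
- **The estimand has a default.** Largely stands. Unlisted events go to treatment policy and visits continue to TP12, so TP6 data remain scheduled. What is missing is confirmation that a missed-draw withdrawal is outside the stopping criteria.
- **The separate rule may be deliberate.** It cannot be excluded, since the protocol labels this a deviation. No rationale is given, however. Unblinded personnel adjudicate stopping, but nothing in the text lets them add the 1-hour condition.

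**Conclusion.** The inconsistency is in the text and is repeated in the synopsis, Protocol 7.4.1.1 and SAP 3.3. As written, the late-value limb withdraws a placebo patient on an untreated-level sUA that would not stop the same patient if drawn on time. The 90-day extension is closed to that patient by the same single threshold. Only these two provisions act differently by arm.

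The size rests on an assumed miss rate of 2, 3 or 5% per draw: at most 10, 14 or 23% of placebo patients over TP1-5, and about 5, 7 or 12% if half the misses have no later value. That a placebo patient cannot meet the 1-hour condition is a strong inference from saline and the entry criterion, not a statement in the plan.

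A reader might infer that the primary comparison is compromised. The documents do not support that: placebo response is assumed to be 5% and power stays above 98%. The effect on the flare, joint and patient-reported endpoints is plausible through earlier ULT, but the documents give nothing to quantify it. The SAP's withdrawal from the study, against the protocol's withdrawal from study drug and the SAP's own statement that visits continue, is a separate conflict. It bears on whether TP6 data are collected.

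**What to change.** - The sponsor should reconcile the two-part stopping rule, the missed-draw paragraph and the 90-day clause in Protocol 7.4.1.1 (with the synopsis and appendix footnotes), Protocol 12.1.8.7, and the corresponding text in SAP 3.3. Which clinical rule applies to a late value or a delayed dose is the sponsor's decision.
- Align SAP 3.3 with the protocol on whether the patient leaves study drug or the study.
- Confirm in SAP 6.1 whether a missed-draw withdrawal counts as meeting the stopping criteria (composite failure) or falls under the treatment-policy default, so that the class does not depend on the draw date alone.

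The cost is protocol and SAP wording. The sample size does not change.

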7.4.2 Criteria for Adjustment or Stopping Doses

An independent Data and Safety Monitoring Board (DSMB) will be formed by charter to assist in reviewing safety data and may provide recommendations to the Sponsor regarding study drug dose adjustment or study termination.

7.5 Criteria for Study Termination

The study can be terminated at any time at the Sponsor's sole discretion. Otherwise, the study will be terminated when all patients have completed follow-up assessments ([Appendix C](#)) or the Sponsor or regulatory agency(ies) have determined there is an unacceptable risk to patients or additional dosing or procedures are not warranted or necessary.

The study may be terminated at a particular investigational site under the following conditions:

- The Investigator fails to enroll patients at an acceptable rate;
- The Investigator fails to comply with pertinent regulations;
- There is insufficient adherence (i.e., compliance) to the protocol;
- Knowingly false information is submitted to the IRB/IEC, Sponsor or designee, or regulatory authorities.

7.6 Study Rationale

7.6.1 Rationale for the Study Design

Refractory gout is a serious condition affecting approximately >200,000 patients in the United States and is characterized by uric acid levels that are not adequately controlled by xanthine oxidase inhibitors, such as allopurinol or febuxostat, or for whom such drugs are contraindicated. About 5% to 10% of gout patients are not treated effectively with allopurinol and thus continue to have acute flares and may experience destructive joint damage and tophus formation (Edwards 2008, Fels 2008). Additionally, approximately 2% of gout patients exposed develop hypersensitivity to allopurinol which can lead to very serious complications and even death (Markel 2005).

Pegloticase (Krystexxa®), a pegylated uricase, was approved by the United States Food and Drug Administration (FDA) in 2010 for the treatment of chronic gout in patients refractory to conventional therapy. Pegloticase is effective in lowering serum uric acid after a single dose. However, >58% of subjects treated with pegloticase experience loss of efficacy within 6 months with the vast majority experiencing loss of efficacy within 3 months due to the formation of anti-drug antibodies (ADAs) with the possibility of infusion reactions, sometimes severe.

SEL-212 is a combination drug product consisting of SEL-037 and SEL-110.36. SEL-037 (pegadricase, pegylated recombinant *Candida utilis* urate oxidase) is an investigational biological therapeutic product presented as a lyophilized pegylated recombinant uricase for intravenous injection. SEL-110.36 is designed to inhibit the formation of ADAs when concomitantly administered with a biologic, specifically, the uricase, pegadricase or SEL-037.

The overall development of SEL-212 remains focused on mitigating the formation of ADAs with the goal of providing a product with better efficacy and safety profiles in patients than the only approved available therapy.

Study SEL-212/301 is a randomized, double-blind, placebo-controlled, parallel-arm study to determine the safety and efficacy of multiple doses of SEL-212 compared to placebo.

A randomized, controlled study is the gold-standard for evaluation of efficacy in clinical research. Randomized, controlled studies are quantitative, comparative, controlled experiments in which treatment effect sizes may be determined with less bias than observational trials. Randomization is considered the most powerful experimental design in clinical trials: with other variables equal between groups, on average, any differences in outcome can be attributed to the intervention.

The blinding scheme in this study will be applied to all patients, Investigators, study personnel, and Sponsor personnel involved in the conduct of the study, except for a designated unblinded statistician who will generate and have access to the randomization codes, a designated unblinded site representative (e.g., pharmacist) who will prepare study drug on the day of treatment, an unblinded infusion nurse who will be responsible for dosing the patient, a designated unblinded medical monitor for assessing the treatment stopping rules, and unblinded drug supply personnel. Blinding and randomization will reduce the potential for treatment bias and will improve the veracity of detected

efficacy and safety signals, particularly in the use of patient-reported quality of life assessments. The parallel arms involving active treatment and placebo will permit adequate statistical comparison of the groups for efficacy and safety signal detection.

Placebo (normal saline) rather than an active control will be employed in this study for ethical and practical considerations. The approved therapeutic for patients with gout refractory to conventional therapy (pegloticase) and the uricase product currently used to treat hyperuricemia (rasburicase) include exogenous enzymes that are highly immunogenic ([Section 5.5](#)) and that would expose patients randomized to an active control group to unnecessary risk. The dosing regimens of the approved enzymes are substantially different from the dosing regimen of SEL-212 and would defeat the steps taken to blind the study. The use of multiple doses of SEL-212 will help determine optimal efficacy: safety profile in a heterogenous population of patients with significant co-morbidities.

7.6.2 Rationale for the Study Population

The selection of this study population ([Section 8](#)) is based primarily on the desired therapeutic indication that the Sponsor will seek. Other selection criteria were set in order to maximize the ability to detect efficacy signals while minimizing any undue risk to the enrolled patients. Therefore, the severity and refractoriness of the patient's disease and sUA level are key Inclusion Criteria ([Section 8.1](#)). In order to enhance the safety of patients on treatment, key Exclusion Criteria involve history of severe allergies or allergies to products that have similar features to the components of SEL-212, medical factors that might be exacerbated while on treatment, and prior exposure to experimental or marketed uricase therapies.

7.6.3 Rationale for the Selected Dose

Dose selection for this Phase 3 study was based on safety and efficacy analyses of the clinical development program for SEL-212, beginning with a completed Phase 1b study (Study SEL-212/101: "A Phase I Single Ascending Dose Safety, Pharmacokinetic and Pharmacodynamics Study of SEL-212 in Subjects with Elevated Blood Uric Acid," NCT02648269) and a Phase 2 study (Study SEL-212/201: "An Open Label Phase II Multiple Dose Safety, Pharmacokinetic and Pharmacodynamics Study of SEL-212 Followed by Open Label Administration of SEL-037 in Subjects with Symptomatic Gout and Elevated Blood Uric Acid" NCT02959918).

7.6.3.1 Phase 1b Study with SEL-212

This was a Phase 1b double-blind, sequential, single-ascending-dose study (SEL-110; Cohorts 1, 3, 5, and 7) combined with an open label, single-ascending-dose study (SEL-212; Cohorts 2, 4, 6, 10, 12 and 14) to assess the safety, tolerability, and PK of SEL-212 and SEL-110. Additionally, the study was to assess the PD (ability to reduce sUA) and immunogenicity (ability to prevent ADAs to uricase and pegadricase) of SEL-212. Generally, patients were dosed on a cohort basis in an ascending stepwise manner. A control group was dosed with SEL-037 only.

In the Phase 1b study (SEL-212/101), patients (N = 64) with a serum uric acid level ≥ 6 mg/dL, with or without a history of gout, were administered SEL-110 alone, SEL-037 (pegadricase) alone, or SEL-212 (SEL-037 + SEL-110) as an intravenous infusion. Mitigation of ADAs and a dose-dependent reduction in

sUA levels occurred from study Day 1 to Day 30 in patients administered SEL-212 (data on file). There was no effect of SEL-110 alone on sUA levels, and patients administered SEL-037 alone developed ADAs that resulted in loss of sUA control by Day 14. SEL-212 was generally well tolerated at all dose levels. The maximum tolerated dose of SEL-110 was determined to be 0.3 mg/kg. Data from this study were used to select additional dose levels of each component of SEL-212 for evaluation in the Phase 2 study SEL-212/201.

7.6.3.2 Phase 2 Studies with SEL-212

7.6.3.2.1 Phase 2 Study SEL-212/201

The Phase 2 study SEL-212/201 was designed as an open-label, ascending multiple-dose study of the combination drug, SEL-212, combined with an open-label, multiple-dose evaluation of SEL-037 (pegadricase) alone in patients with symptomatic gout and elevated blood uric acid. Part A of the study consisted of three 28-day treatment cycles of SEL-212, which was then followed by Part B, which consisted of two 28-day treatment cycles of SEL-037 alone, with a primary objective of assessing the safety, tolerability, PK, PD of SEL-212 (i.e., the combination of SEL-110 and SEL-037). Additional assessments include the ability of SEL-212 to reduce serum uric acid levels and prevent anti-drug antibodies to uricase and pegadricase. Part C of the study consisted of 5 monthly doses of SEL-212.

In Study SEL-212/201 with SEL-212, sUA levels remained consistently below 6 mg/dL in 70% to 89% of evaluable Part A patients administered SEL-212 once monthly for 3 months. The control of sUA occurred in the context of low incidences of infusion reactions, anaphylaxis, and gout flares as well as treatment-emergent adverse events (TEAEs) known to be potentially associated with rapamycin (sirolimus – Rapamune®). Data support a once monthly dosing regimen. For cohorts 7-12 with SEL-110 doses of 0.1 mg/kg or higher, 46% of evaluable patients had sUA <6 mg/dL at week 20.

In Part C cohorts receiving 5 monthly doses of SEL-212, 61%, 71%, and 67% of eligible patients in Cohorts 13, 15, and 17, respectively, maintained sUA control (sUA, <6 mg/dL) at week 12 without the development of ADAs. All 21 patients in cohorts 13, 15 and 17 who had sUA < 6 mg/dL at week 12, maintained sUA control through the end of treatment period 5 and had sUA < 6 mg/dL at week 20.

The efficacy signal of SEL-212 in SEL-212/201 persists across multiple treatment cycles in all cohorts and through all 5 treatment cycles when SEL-212 is given at each treatment, as demonstrated by dose-dependent reductions in sUA levels below 6 mg/dL and ADA suppression in conjunction with increasing SEL-110 dose levels up to 0.15 mg/kg.

Cohorts 7, 11, 13 and 17 represent the dose regimens that will be evaluated in the Phase 3 program (0.1 or 0.15 mg/kg SEL-110 and 0.2 mg/kg SEL-037). Part C cohorts 13, 15, and 17 received 5 once monthly doses of SEL-212, and patients in the proposed Phase 3 program will receive a total of 6 or 12 once monthly doses of SEL-212.

Across cohorts 1 to 17, 28 SAEs have been reported in 20 of 152 (13.2%) patients. They include 9 infusion reactions reported as related or possibly related to SEL-212. Of these 9 infusion reactions, only

3 occurred during repeat dosing of SEL-212 in cohorts 7, 13 and 17; 4 occurred in cohorts that received SEL-037 alone or SEL-037 with the lowest dose of SEL-110 (0.05 mg/mL); and 2 were due to dosing errors. All SAEs were successfully treated without complication. No study drug related SAEs or discontinuations involving gout flares, metabolic disorders, hypophosphatemia, or changes in lipid levels have been reported in the Phase 2 study SEL-212/201.

Leukopenia can be seen in patients taking high doses of rapamycin for extended periods of time. Leukopenia was reported by investigators in 11 (7.2%) and neutropenia in 6 (3.9%) of patients. One patient's neutropenia was reported as severe but not identified with a TEAE of infection. No SAEs or study drug discontinuations involving leukopenia or neutropenia have been reported.

Another TEAE seen in patients taking oral rapamycin is stomatitis (mTor Inhibitor associated stomatitis-mIAS) and was observed in the SEL-212 Phase 2 trial at a lesser rate than seen in previous clinical trials ([Peterson 2016](#)). Stomatitis or aphthous ulcers were reported in 19 (12.5%) of patients; all were mild or moderate in severity. The TEAEs categorized as stomatitis or oral lesions did not result in any SAEs, study drug discontinuations, or withdrawals. All resolved with minimal topical oral treatment of corticosteroids.

Additional TEAEs of particular interest for rapamycin are hyperglycemia, hypophosphatemia, and hypertriglyceridemia. These were reported in 5.9%, 3.9% and 17.8% of patients in the SEL-212 Phase 2 trial, respectively. These TEAEs resolved without any medical intervention, their duration was transient, and they did not result in any SAEs, study drug discontinuations, or withdrawals.

